3.2. Primary Endpoint

Proportion of peanut allergic subjects who pass a DBPCFC after the 3-month avoidance period (Week 117 or equivalent) following the end of active treatment phase

3.3. Secondary Endpoints

- Proportion of PA subjects who pass a DBPCFC after a 6-month avoidance period.
- Proportion of PA subjects who pass a DBPCFC after a 9-month avoidance period.
- Proportion of PA subjects who pass a DBPCFC after a 12-month avoidance period.
- Proportion of PA subjects who can successfully complete the build-up phase of peanut OIT to the highest dose (4,000 mg of peanut protein) with only mild Objective **APPENDIX 4**symptoms
- Proportion of PA subjects who can successfully undergo the build-up and maintenance phases of peanut OIT with only mild symptoms.
- Comparison of the proportion of subjects in placebo, avoidance, and 300 mg peanut protein/day groups who are able to undergo OFCs with no clinical reactivity after initiating OIT.

Sub Study GI Endpoint

• Proportion of PA subjects who show increased immune cells consistent with immune tolerance (i.e. regulatory T cells) vs inflammatory allergy (i.e. eosinophils, mast cells) over time points obtained with GI biopsy tissues.

3.4. Stratification, Randomization, and Blinding/Masking

Randomization will occur in a 2 by 2 block design performed by [name] using a computerized system.

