3.1. Description of Study Design

A Phase 2, single-center, randomized double blind, placebo controlled study of the induction of peanut tolerance by oral immunotherapy (OIT). Our intent to treat population will be 120 subjects, ages 7-55 years, with an allergy to peanut, as determined by DBPCFC, history, clinical symptoms, and positive skin prick test (SPT). Please see Figure 1.

First, subjects will be screened (Part I, Figure 1). The 120 enrolled subjects will be randomized 2.4:1.4:1 (please see section 13). Thus, there will be three arms: (1) Arm A on peanut OIT until week 104 and once meeting criteria *[i.e. 1) on OIT treatment for minimum 104 weeks, 2) taking daily maintenance dose of 4,000 mg protein for at least 13 weeks, 3) no severe reactions (Grade 3, APPENDIX 4) to home dosing from Week 92-Week 104, and/or 4) no objective reactions, (Appendix 4) at the Week 104 DBPCFC]* has been assigned to avoid peanut (i.e. 600 mg oat flour). (2) Arm B on peanut OIT until week 104 and once meeting criteria, has been assigned to be maintained on 300 mg peanut protein (i.e. 600 mg oat flour). (3) Arm C that is maintained on placebo (oat flour) and once meeting criteria, will receive 600 mg oat flour beginning on week 104. This will be true even if a subject in the placebo group meets criteria at week 104. This way all participants will receive approximately the same volume of flour so that the subject blinding will be easier to maintain. The decision to maintain subjects on only 300 mg peanut protein after week 104 is for ease of eating peanut and to test if a lower amount of protein can still maintain desensitization. This upfront randomization is performed because our statistical analysis plan is focused on an intent to treat analysis.

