13.1 Overview

This double blind, randomized, placebo controlled study in peanut-allergic children and adults intends to identify basic immune mechanisms that explain the effects of OIT in individuals who do or do not become clinically tolerant and to determine whether immune monitoring can predict safety and outcomes in OIT protocols.

The 120 enrolled subjects will be randomized 2.4:1.4:1. Thus, there will be three arms: (1) Arm A (60 subjects) on peanut OIT until week 104 and once meeting criteria [*i.e.* 1) assigned to OIT treatment for minimum 104 weeks, 2) reaching maintenance 13 weeks prior to DBPCFC at week 104 3) no severe reactions (Grade 3, APPENDIX 4) to home dosing from Week 92-Week 104, and/or 4) no objective reactions, (Appendix 4) at the Week 104 DBPCFC] has been assigned to avoid peanut (i.e. 600 mg oat flour). (2) Arm B (35 subjects) on peanut OIT until week 104 and once meeting criteria, has been assigned to be maintained on 300 mg peanut protein (i.e. 600 mg peanut flour). (3) Arm C (25 subjects) that is maintained on placebo (oat flour) and once meeting criteria, will receive 600 mg oat flour beginning on week 104. This will be true even if a subject in the placebo group meets criteria at week 104. This way all participants will receive approximately the same volume of flour so that the subject blinding will be easier to maintain. The decision to maintain subjects on only 300 mg peanut protein after week 104 is for ease of eating peanut for so long. This upfront randomization is performed because our statistical analysis plan is focused on intent-to-treat principles.

The primary analysis is an intent-to-treat comparison of success rates between arms A and C, where success is defined by reaching and passing the DBPCFC at both 104 weeks and 117 (or equivalent) weeks.

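### The block design named in Section 3.4 does not fit the upfront three-arm 2.4:1.4:1 allocation, and Section 8.3 gives a third account of the randomization

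*Protocol*

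**What the plan says.** The protocol describes the randomization in three places.

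- **Section 3.4** (method): "Randomization will occur in a 2 by 2 block design", carried out by a named role using a computerized system. The term is not explained, and no block composition is given.
- **Section 3.1** (ratio and timing): "The 120 enrolled subjects will be randomized 2.4:1.4:1". It adds: "This upfront randomization is performed because our statistical analysis plan is focused on an intent to treat analysis". The synopsis repeats the ratio, and Figure 1 places randomization to Arms A, B and C before the Initial Dose Escalation Day. Section 13.1 gives the arm sizes: "there will be three arms: (1) Arm A (60 subjects) on peanut OIT", "2) Arm B (35 subjects) on peanut OIT until week 104" and "3) Arm C (25 subjects) that is maintained on placebo (oat flour").
- **Section 8.3** (study visits): subjects who have met the week-104 criteria are then randomized 1:1 to avoidance or to the 300 mg group.

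Section 13.7 bases the power of the primary A versus C comparison on 60 and 25 subjects. Section 3.5.2 keeps the randomization lists in the pharmacy, accessible only to the unblinded pharmacists and inspected by the site monitor.

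**The concern.** A 2 by 2 block is most naturally read as blocks of two, blocks of four, or two groups of two. None of these is a three-arm scheme at 12:7:5. Someone building the list from Section 3.4 would have to add a rule that the protocol does not contain, and someone working from Section 8.3 would form Arms A and B at a different time and in a different ratio.

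This is more than a detail left for later, because the protocol states a method and that method conflicts with the design stated elsewhere in the same document. What is at stake is whether the protocol determines how Arms A, B and C come about. The intent-to-treat comparison of A with C depends on that. Under the Section 8.3 account, a subject who fails before week 104 would never be assigned to A or B, so Arm A would have no clear intent-to-treat denominator.

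A secondary matter is concealment: in a single-centre trial, a small fixed block size that can be read in the protocol gives some help to anyone trying to guess the next assignment.

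**Working it through.** **1. The plan's own figure.** Inputs from Section 13.7: success rates 0.35 (A) and 0.05 (C), two-sided alpha 0.05, n = 60 and 25. Pooled-variance normal approximation:

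power = Φ{ [|pA − pC| − 1.96·√(p̄(1−p̄)(1/nA + 1/nC))] / √(pA(1−pA)/nA + pC(1−pC)/nC) }

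- p̄ = (60×0.35 + 25×0.05)/85 = 22.25/85 = 0.262
- null standard error = √(0.262×0.738×(1/60 + 1/25)) = 0.1046
- alternative standard error = √(0.2275/60 + 0.0475/25) = 0.0754
- power = Φ[(0.30 − 1.96×0.1046)/0.0754] = Φ(1.26) = 89.6%

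Exact enumeration gives 91.5% for the pooled z test and 89.2% for Fisher's test. The stated 90% reproduces, and all 15 cells of the power table agree within one point.

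**2. The allocation.** 2.4 + 1.4 + 1 = 4.8 and 120/4.8 = 25, so the arms are 2.4×25 = 60, 1.4×25 = 35 and 1×25 = 25. The greatest common divisor is 5, giving 12:7:5, which sums to 24.

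**3. Which identical repeated blocks fit.** Each block must hold whole numbers of A, B and C in proportion 60/120, 35/120 and 25/120.

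| Block size | A | B | C | Fits? |
|---|---|---|---|---|
| 2 | 1.00 | 0.58 | 0.42 | no |
| 4 | 2.00 | 1.17 | 0.83 | no |
| 24 | 12 | 7 | 5 | yes (5 blocks) |

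Up to 120, only 24, 48, 72, 96 and 120 fit.

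**4. What blocks of four would give.** Thirty AABC blocks give 60:30:30, which is five fewer in B and five more in C than planned. Two successive equal splits give 60:30:30 or, if the first split is peanut versus placebo, 30:30:60 for A:B:C. None of these is 60:35:25.

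**5. Effect on A versus C.**

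- At 60:30, p̄ = 22.5/90 = 0.25, the standard errors are 0.0968 and 0.0733, and power = Φ[(0.30 − 0.1898)/0.0733] = Φ(1.50) = 93%.
- As an illustration of the 1:1 account, assume all 95 peanut subjects reached the criteria and were split equally. Arm A would hold 47 or 48, and power against 25 would be about 87%. For n = 47 this is Φ[(0.30 − 1.96×0.1066)/0.0821] = Φ(1.11).

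**6. Predictability.** Assume the block size and every earlier assignment in the block are known. The share of assignments then fully determined is:

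- AB: 1/2 = 50%
- AABB: the last place always, plus one more when the last two match (probability 1/3), so (1 + 1/3)/4 = 33%
- AABC: the same reasoning with probability 1/6, so (1 + 1/6)/4 = 29%
- a block of 24 at 12:7:5: about 7% (by simulation)

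**The case against.** A reader might infer that blocks of four make 60:35:25 impossible. The documents do not support that. Section 3.4 gives no block composition, and 25 AABC blocks plus 5 AABB blocks total A = 50 + 10 = 60, B = 25 + 10 = 35 and C = 25. Impossibility holds only for identical repeated blocks. The protocol describes no such mix, however, so the inconsistency stands.

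A reader might also infer that upcoming assignments are easy to guess. That needs knowledge of earlier assignments. The trial is double blind, packaging and labelling are identical, and only unblinded pharmacists can reach the lists. Arms A and B take the same peanut product until week 104, so dosing reactions could hint at peanut versus placebo but could not separate A from B before then. What remains is a conditional weakness: a guess from reactions, or an emergency unblinding, would be worth more with small fixed blocks.

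Finally, no harm to the primary power is shown. It is right at 60 versus 25 and would rise under 60:30:30, where the loss would be five Arm B subjects in the A versus B comparison, which is supportive. This objection stands in full and limits the point to the description of the method.

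The absence of an exact block size from the protocol is not a fault; that belongs in a restricted document.

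**Conclusion.** The point holds as an inconsistency. Read as blocks of two, blocks of four or two groups by two, Section 3.4 does not match the single upfront 12:7:5 randomization in Sections 3.1 and 13.1, and the 1:1 statement in Section 8.3 conflicts with both. The size depends on which passage is followed: 60:30:30 under AABC blocks, or roughly equal A and B under Section 8.3, against the planned 60:35:25. The conclusion assumes that blocks are repeated with the same composition, since the protocol describes nothing else.

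Concealment is secondary and conditional, and the 29% to 50% figures apply only if earlier assignments in the block are known. The 90% power statement is not in error. It would also go too far to conclude that the list actually in use is wrong: the documents do not show how it was built, only that the text does not settle it.

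**What to change.** Replace the sentence in Section 3.4 with:

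> Subjects are randomized once, before the Initial Dose Escalation Day, to Arms A, B and C in the ratio 12:7:5 (60:35:25) using computer-generated permuted blocks compatible with that ratio; block sizes are kept in a restricted document not available to clinical staff.

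Reconcile the 1:1 statement in Section 8.3 with the upfront randomization, so that the protocol gives one account of when and in what ratio Arms A and B are formed. Then have someone outside the clinical team check that the list in use follows the stated scheme.

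The cost is two sentences and one check, with a new list needed only if the check fails. There is a small downside: if accrual stops in the middle of a block, the arm sizes may depart slightly from 12:7:5.

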3.4.1. Procedure for Unblinding/Unmasking

Unblinding must be approved by the study NIAID Medical Monitor unless an immediate life-threatening condition has developed and the NIAID Medical Monitor is not accessible. In all cases of unblinding, the site investigator will notify the NIAID Medical Monitor within 24 hours. The emergency unblinding will also be reported to the Data and Safety Monitoring Board (DSMB).

A full account of the event will be recorded, including the date and time of the unblinding, the reason for the decision to unblind, and the name of the individual who made the decision and the names of the Medical Monitor and others who were notified.

Unblinding the study due to an approved interim analysis, final analysis, or study termination will require written approval from NIAID.

3.5.2 Securing Blinding and Randomization Information

Randomization lists are maintained in a secured area, the pharmacy, by the individuals responsible for maintaining the blind, the unblinded pharmacists. The PPD site monitor (Clinical Research Associate) inspects the lists at each site visit to ensure they remain in the secured pharmacy, only accessible by the unblinded pharmacists. In the case of unscheduled unblinding or the removal of the randomization lists from the secured pharmacy binder, the Clinical Research Associate will verify that the site Principal Investigator and the NIAID Medical Monitor have been notified and that a written account has been completed and forwarded to these individuals.

4. Selection of Participants and Clinical Sites/Laboratories

4.1. Rationale for Study Population

The lower cutoff of 7 years of age was selected to include only subjects with sufficient blood volumes (to perform the mechanistic studies we need blood every 3 months or per schedule of events (+ or - 1 clinic visit). We have included a weight cut off of 17 kg so that we are compliant with IRB and NIH guideline—i.e. (for children: 5 ml/kg at any single draw, no more than 9.5 ml/kg over an 8-week period; adults: the smaller of 10.5 ml/kg or 550 ml total at any single draw). The upper age limit of 55 years was selected to ensure that the patients do not have underlying cardiovascular conditions that could preclude the use of epinephrine in subjects exposed to the risk of anaphylaxis.

Cross-reactivity between peanut and grass pollen may affect the SPTs performed to peanut. All subjects will be screened for appropriate environmental allergen sensitivity by SPT.

4.2. Inclusion Criteria

Individuals who meet all of the following criteria are eligible for enrollment as study participants:

- 1. Subject and/or parent guardian must be able to understand and provide informed consent and/or assent as applicable.
- 2. Peanut-allergic subjects between the ages of 7-55 years old.
- 3. Weight equal or greater than 17 kg.
- 4. Sensitivity to peanut allergen as documented by a positive skin prick test result (5 mm or greater diameter wheal relative to negative control) within 6 months preceding enrollment.
- 5. Allergy to peanut based on a double-blind placebo-controlled oral food challenge (DBPCFC) (see **Appendix 4** for scoring details) failed at a cumulative dose ≤500 mg peanut protein within 6 months preceding enrollment.
- 6. All female subjects of child-bearing potential will be required to provide a blood sample for pregnancy testing that must be negative one week before being allowed to participate in the study.
- 7. Subjects must agree to remain in the study area during the trial.
- 8. Subjects must be trained on the proper use of the EpiPen and patient comprehension should be confirmed (see **Appendix 5)** to be allowed to enroll in the study.
- 9. Subjects with other food allergies must agree to eliminate these other food items from their diet so as not to confound the safety and efficacy data from the study.
- 10. Female subjects of child bearing potential must agree to use birth control for the duration of the study.

4.3. Exclusion Criteria

Individuals who meet any of these criteria are not eligible for enrollment as study participants:

- 1. Inability or unwillingness of a participant to give written informed consent or comply with study protocol
- 2. History of uncontrolled cardiovascular disease
- 3. History of other chronic disease (other than asthma, atopic dermatitis, or rhinitis) requiring therapy (e.g., heart disease, diabetes) that, in the opinion of the Principal Investigator, would represent a risk to the subject's health or safety in this study or the subject's ability to comply with the study protocol
- 4. History of eosinophilic gastrointestinal disease
- 5. Current participation or participation within the last 6 months in any other interventional study.
- 6. Subject is on 'build-up phase" of immunotherapy to another allergen (i.e., has not reached maintenance dosing)
- 7. Severe asthma (2007 NHLBI Criteria Steps 5 or 6) at time of enrollment
- 8. Mild or moderate (2007 NHLBI Criteria Steps 1-4) asthma at time of enrollment with any of the following criteria met:
 - a. FEV1 < 80% of predicted, or FEV1/FVC < 75%, with or without controller medications (only for age 6 or greater and able to do spirometry) *or*
 - b. ICS dosing of > 220 mcg daily fluticasone (or equivalent inhaled corticosteroids based on NHLBI dosing chart) or
 - c. 1 hospitalization in the past year for asthma or
 - d. ER visit for asthma within the past six months
- 9. Use of steroid medications (IV, IM or oral) in the following manners for asthma
 - a. history of daily oral steroid dosing for >1 month during the past year or

- b. burst or steroid course in the past 3 months or
- c. >2 burst steroid courses in the past year
- 10. Use of complementary and alternative medicine (CAM) treatment modalities (e.g., herbal remedies) for atopic and/or non-atopic disease within 90 days preceding Initial Dose Escalation Day (IDED) or at any time after the IDED
- 11. Inability to discontinue antihistamines for the Initial Dose Escalation Day, skin testing or OFCs
- 12. Use of omalizumab within the past six months, or immunomodulator therapy (not including corticosteroids)
- 13. Use of β-blockers (oral)
- 14. Pregnancy or lactation
- 15. History of sensitivity to oat
- 16. History of severe anaphylaxis to peanut with symptoms including hypotension requiring fluid resuscitation and/or the need for mechanical ventilation
- 17. Use of investigational drugs within 24 weeks of participation
- 18. Past or current medical problems or findings from physical assessment or laboratory testing that are not listed above, which, in the opinion of the investigator, may pose additional risks from participation in the study, may interfere with the participant's ability to comply with study requirements or that may impact the quality or interpretation of the data obtained from the study.

5. Known and Potential Risks and Benefits to Participants

5.1. Risks of Investigational Product or Intervention as cited in Investigator Brochure or Package Insert

There is no IB or Package Insert for the peanut flour.

5.2. Risks of Investigational Product or Intervention cited in Medical Literature and/or those based on the Investigators' experience

In patients with peanut allergy, there have been many oral immunotherapy studies performed using procedures and dosing similar to those proposed in this Phase 2 study. In general, safety profile has been very good across the studies, and based on those studies approximately 80%, 15% and <1% of the subjects are expected to have a mild, moderate or severe symptoms, respectively, during some point in their dosing with the peanut immunotherapy. It is important to note that essentially all adverse events have been allergy-related, predictable, and reversible. The only major atypical adverse event has been several reported cases of eosinophilic esophagitis, reversible upon cessation of dosing.

Specifically, the buildup and daily maintenance doses of peanut OIT may cause allergic symptoms including sneezing, rhinorrhea, urticaria, angioedema, flushing, flares of eczema, ocular, nasal, oral and/or throat pruritus, nausea, vomiting, abdominal discomfort, cough, wheezing and/or shortness of breath in addition to severe anaphylaxis. Although no subject will be allowed to enroll who carries the diagnosis of eosinophilic disorder, the risk of eosinophilic esophagitis during OIT will be evaluated during the study³⁷⁻³⁸. The likelihood of a subject experiencing any allergic symptoms is expected to be lessened by initiating dosing at extremely small amounts of characterized peanut allergen and by buildup dosing under observation in a clinical setting until the maintenance dose is achieved.

Oral food challenges may induce an allergic response. Allergic reactions can be severe including life-threatening allergic reactions; however, the risk of an allergic reaction is reduced by initiating the challenge with a very small amount of the food, gradually increasing the dose, and stopping the challenge at the first sign of a reaction. If subjects have an allergic reaction during the challenges, they may need oral, intramuscular, or intravenous medications. Subjects will have an IV catheter placed before the OFCs if they have a history of anaphylaxis with hypotension requiring IV fluid resuscitation. Additionally, IV catheters may be placed, at physician discretion for any visit, based on factors such as previous reactions, recent clinical history, and clinical status observed at the visit. Trained personnel, including a study physician,

as well as medications and equipment, will be immediately available to treat any reaction. The anticipated rate of life threatening anaphylactic reactions would be < 0.1%.

There may be a risk that during participation in the trial the subjects may decrease their vigilance against accidental peanut ingestion because they believe they are protected from it. This phenomenon has been reported in previous trials, and subjects in the trial will be warned that they should continue to practice their usual vigilance against accidental ingestion of peanuts or peanut-containing foods.

5.3. Risks of Other Protocol Specified Medications

Anti H-1 blockers (e.g., cetirizine, loratadine, fexofenadine) will be used orally according to manufacturer's instructions approximately one hour prior to each food allergen dose at home. The risks of these medications include:

- Central nervous system: Headache, fatigue, somnolence, drowsiness, insomnia, sleep disorders, dizziness, muscle pain
- Gastrointestinal: Diarrhea, nausea, vomiting, dyspepsia, abdominal pain, dry mouth
- Neuromuscular & skeletal: Myalgia, back pain, pain in extremities
- Hypersensitivity reactions (anaphylaxis, angioedema, chest tightness, dyspnea, flushing, pruritus, rash, urticaria)

5.4. Risks of Study Procedures

A potential risk associated with the Initial Dose Escalation Day procedure, updosing procedure, and oral food challenges is the risk of anaphylaxis. Symptoms of anaphylaxis may include pruritus, urticaria, angioedema, wheezing, cough, dyspnea, emesis, diarrhea, and hypotension that may progress to hypotensive shock.

The potential discomforts with the Initial Dose Escalation Day procedure, updosing procedure, and oral food challenges are no more than when eating the suspected food in the past. Symptoms are usually transient lasting less than 2 hours and include pruritus, urticaria, nausea, abdominal discomfort, emesis and/or diarrhea, rhinitis, and sneezing and/or wheezing. The major risks involved include respiratory distress and rarely anaphylactic shock. Medication, personnel, and equipment are immediately available in the CFRU to treat allergic reactions. Subjects will be provided a prescription for an EpiPen[®] or EpiPen, Jr.[®] or equivalent to have with them at all times and to use in case of an allergic reaction.

Risks associated with phlebotomy or insertion of an intravenous catheter include infection, syncope, and localized pain, stinging, bleeding, or contusions at the phlebotomy site where the needle is inserted into the vein.

The risk involved with skin testing includes discomfort from the needle prick, along with pruritus and swelling at the skin test site in positive responses. Less common side effects include severe allergic reactions.

There may be an increased risk of developing Eosinophilic esophagitis (EoE), which is an immune-mediated disease as a result of inflammation of the esophagus. Symptoms range by age, with children potentially presenting with feeding difficulties, abdominal pain, and/or vomiting and adults may experience chest pain, food getting "stuck", and/or abdominal pain. If these symptoms are present, an endoscopy will be needed to confirm diagnosis, which may be performed by a gastroenterologist.

The risks involved with the GI Sub-study endoscopy are rare and include bleeding, perforation of the esophagus, stomach or duodenum, sepsis and pneumonia. The risks associated with the biopsy procedure include bleeding and perforation of the esophagus, stomach and duodenum. The risks associated with the use of the FDA approved medications routinely used for standard of care endoscopies (fentanyl, midazolam and Benadryl) include respiratory depression, constipation, dry mouth, dizziness, blurred vision, sleepiness and agitation.

